11	7.	Immune response including prevalence of hypersensitivity-related outcomes (e.g., asthma, atopic
12		dermatitis; higher levels of immunoglobulins (IgG, IgA and IgM) and lower antibody responses to
13		rubella, mumps, and diphtheria vaccines).
14	Neuroo	developmental outcomes (lower intelligence quotient (full scale IQ), attention-deficit and
15	hypera	ctivity disorder (ADHD).
16	For adu	ults (aged \geq 18 years), the Multi-site Study will evaluate the following main hypotheses.
17	Higher	serum levels of PFOA, PFOS, PFHxS, or other PFAS are associated with:
18	1.	Lipids (higher total cholesterol, low-density lipoprotein and triglycerides) and a higher prevalence
19		of hypercholesterolemia).
20	2.	Higher prevalence of coronary artery disease and hypertension (including hypertensive disorders
21		of pregnancy).
22	3.	Renal function (higher level of uric acid and a higher prevalence of hyperuricemia, lower
23		estimated glomerular filtration rate (eGFR)) and higher prevalence of kidney disease.
24	4.	Glycemic parameters (glucose, insulin, glycosylated hemoglobin (HbA1c), auto-antibodies (GAD-
25		65 and IA-2), C-peptide, pro-insulin) and diabetes (type 1 and 2).
26	5.	Differences in thyroid hormones (thyroid stimulating hormone (TSH), TT4, FT4, and TT3), and
27		higher prevalence of hypothyroidism/ hyperthyroidism.

1	6.	Liver function/damage biomarkers (alanine transaminase (ALT), γ -glutamyltransferase (GGT),
2		direct bilirubin, cytokeratin-18 (CK-18)) and liver disease.
3	7.	Higher prevalence of osteoarthritis and osteoporosis.
4		
5	8.	Higher prevalence of endometriosis.
6	9.	Measures of immune response and inflammation (serum levels of IgA, IgE, IgG, IgM, C - reactive
7		protein (CRP), antinuclear antibodies (ANA), inflammatory cytokines and adipokines (interleukin
8		1- β (IL-1 β), interleukin 6 (IL-6), interleukin 8 (IL-8), monocyte chemotactic protein-1 (MCP-1),
9		tumor necrosis factor α (TNF α), leptin, adiponectin, resistin, plasminogen activator inhibitor-1
10		(PAI-1).
11	10	Higher prevalence of autoimmune diseases such as ulcerative colitis, rheumatoid arthritis, lupus,
12		and multiple sclerosis.
13		
14	2.6 Int	ended Use of Study Findings
14	2.0 m	
15	Given t	hat epidemiological research on the health effects of drinking water exposures to PFAS other than
16	PFOA i	s at an early stage, the Multi-site Study should make an important contribution to the scientific

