7 3.6.2.3 Adult Consent

Before any data collection can begin in the adult study, trained study staff will review the hardcopy Adult
Consent Form with the interested recruit (Attachment 7b4). The study staff will explain the purpose of
the study and obtain written informed consent for the completion of a questionnaire, the collection of a
new fasting blood specimen, the storage of this blood specimen for future analyses, access to medical
records (Attachment 7b5), and permission to contact the participant in the future for a possible study .
After signing the consent form, the adult will become a study participant.

14

15 3.6.2.4 Risks and Benefits

As further described in **Section 3.8.1**, the recipient will inform the participant that his or her participation is protected by a Certificate of Confidentiality under Section 301(d) of the Public Health Service Act as amended by Section 2012 of the 21st Century Cures Act. The recipient will further inform the participant that access to identifiable occupational history, private medical records, and to school records are protected from certain disclosures under Section 301(d) of the PHSA.

The risks of participation in this study are minimal (defined in 45 CFR 46.110). In-home urine collections are minimal risk. This study plans for a one-time 23-ml (5 teaspoons) volume of fasting blood collected from the child and a one-time 33-ml volume of fasting blood collected from the adult. These amounts of blood are the minimum necessary to conduct analyses for PFAS and the effect biomarkers (**Attachment 2**). After the blood draw, the participant will be offered a small snack, thereby allowing monitoring of adverse events due to phlebotomy.

Participants in this study will not receive any direct benefit from taking part in this research. Their taking part in this research will provide the scientific community and the public a better understanding of how exposures to PFAS-contaminated drinking water may affect human health. Each adult participant and the parent of the child participant will receive the results of the analyses of serum PFAS levels and effect
- 1 biomarkers. They will receive the results of their urine PFAS and effect biomarker levels, if ATSDR identifies
- 2 meaningful urinary analyses to perform.

3 **3.6.3 Update Contact Information and Medication List**

The adult participant and the parent of the child participant will be asked to verify and update his or her

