3 kidney function, sex hormones, and immune function (Attachment 2):

5	٠	Uric acid, creatinine,
6	•	Thyroxine (TT4, FT4), T3, thyroid stimulating hormone (TSH),
7	•	Glucose, insulin, glycosylated hemoglobin (HbA1c), auto-antibodies (GAD-65 and IA-2), C-peptide,
8		pro-insulin,
9	٠	Alanine transaminase (ALT), γ -glutamyltransferase (GGT), direct bilirubin, and cytokeratin-18 (CK-
10		18),
11	٠	Testosterone, estradiol, sex hormone-binding globulin (SHBG), follicle stimulating hormone,
12		insulin-like growth factor,
13	٠	Immunoglobulin G (IgG), IgA, and IgM; antibodies to measles, mumps, rubella, tetanus, and
14		diphtheria.

15 The child study will use the cut points of 50 ng/dL of total testosterone and 20 pg/mL of estradiol to identify sexual maturation in boys and girls, respectively (Lopez-Espinosa 2011). The child study will 16 17 measure IgG antibodies for measles, rubella, and diphtheria to determine vaccine responses. It will analyze allergen-specific IgE (mold, dust mites, dog, cat, cow's milk, peanut, hen's egg, and birch). The 18 19 study will analyze serum levels of thyroid stimulating hormone (TSH) and total/free T4 separately and use 20 these measurements to determine clinical and subclinical hypothyroidism and hyperthyroidism. The 21 study will measure uric acid, total cholesterol, low-density and high-density lipoprotein, and triglycerides. 22 We also propose to measure liver enzymes and CK-18 (Feldstein 2013, Mora 2018, and Santoro 2013).

23 3.7.2 Adults

- 24 The study will analyze the following biomarkers in the adult fasting serum (Attachment 2):
- Total cholesterol, low density lipoprotein, high density lipoprotein, total triglycerides,
- Uric acid, creatinine,
- Thyroxine (TT4, FT4), T3, thyroid stimulating hormone (TSH),
- Glucose, insulin, glycosylated hemoglobin (HbA1c), auto-antibodies (GAD-65 and IA-2), C-peptide,
 pro-insulin,

- Alanine transaminase (ALT), γ-glutamyltransferase (GGT), direct bilirubin, and cytokeratin-18 (CK 18),
- Immunoglobulin G (IgG), IgA, IgE and IgM; C reactive protein, and antinuclear antibodies (ANA),
 - Cytokines and adipokines (e.g. IL-1β, IL-6, IL-8, MCP-1, TNFα, leptin, adiponectin, resistin, PAI-1).

5 3.7.3 Quality Control/Quality Assurance

4

To maintain the integrity of the lab results, a backup generator will be available for the refrigerator and
freezer at the study office. All serum, blood, and urine specimens will be securely stored at the study office

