				Luteal: 1.8-5.1 IU	J/L
				Postmenopausal	: 16.7-113.6 IU/L
Insulin-like growth factor (IGF-1)					
	Follicle stimulating hormone (FSH) Stage IV Stage V ADULTS Males: 10-57 nm Remales (non-pr Males? 4-6 years: < or =				

⁹ https://www.mayomedicallaboratories.com/test-catalog/Clinical+and+Interpretive/8670

Laboratory and Contact	tory and Analyte		Matrix	Volume	Reportable Range, Guidelines, Critical Values Reference ranges will be updated when commercial lab is selected.
Children and Adults		-		2	
Commercial	Immune Function				
Laboratory (to be determined)* Contact:	lg A, lg G, lg M, lg E		Serum	1 ml	
	Glycemic Parameters				
Commercial	Glycosylated hemoglobin (HbA1c)		Whole Blood EDTA	1 ml; plus 1 ml reserve	Diabetes Risk¹⁰ Normal: <5.7% Increased Risk Diabetes: 5.7-6.4% Diabetes: ≥6.5% (confirmation required)
Laboratory (to be	Glucose, fasting, 8-hour Insulin			0.5 ml	
determined)*				Glucose/	<17 μU/ml ⁸
contact:	Glutamate Decarboxylase -65 (Anti-GAD 65)		Serum	Insulin; 1 ml	Negative Antibody: DK≤33 ⁸ Positive Antibody: DK>33
	Thurseine Dheenhetere like Drotein Autoentihedies (Anti 142)			antibodie	Negative Antibody: DK<5 ⁸
	myrosine prosphatase-like protein Autoantibodies (Anti-IAZ)			S	Positive Antibody: DK≥5
Children Only					
Commercial Laboratory (to be determined)* Contact:	Antibodies to measles, mumps, rubella, tetanus, and diphtheria	Yes	Serum	1 ml	
		Serum - 9n Red Top 2	nl Whole Blood – 2 ml Urine – 16 ml x10 ml EDTA Lavender Top 3 ml		

Adults Only				
	Autoimmune Parameters	Yes	Serum	

¹⁰ American Diabetes Association. Standards of Medical Care in Diabetes - 2011. Diabetes Care. January 2011;34(Supplement 1):S11-S61 (subject to periodic update).

	Rheumatoid Factor (RF)				< 15 IU/mL ¹¹
Commercial Laboratory (to be determined)* Contact:	Antinuclear Antibody (ANA) screen			2 ml (for all)	< or =1.0 U (negative) ¹² 1.1-2.9 U (weakly positive) 3.0-5.9 U (positive) > or =6.0 U (strongly positive)
	Antinuclear Antibody (ANA) titer				
		ļ	Adult Total	Serum – 1 Red Top 3	L ml Whole Blood – 2 ml Urine – 16 ml x 10 ml EDTA Lavender Top 3 ml

 ¹¹ https://www.mayomedicallaboratories.com/test-catalog/Clinical+and+Interpretive/9060
 ¹² https://www.mayomedicallaboratories.com/test-catalog/Clinical+and+Interpretive/9026

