Attachment 8.

Thank you so much. To get you prepared for the appointment, I have just one more question about some medicines [you/your child/both you and your child] might be taking now.

- Are [you/your child/either you or your child] taking any medication for diabetes?
 - YES > Because [you/your child/both you and your child] take diabetes medication, we want to give special instructions about your appointment(s). We will be mailing out a reminder card. If [you/your child/both you and your child] can fast and take your medication without eating, please do. If [you/your child/both you and your child] cannot fast, please eat, and take your medications as usual. Please eat only fat-free or low-fat food, if possible. Please write down the time and the foods you eat. You may drink water during this time. [GO TO CLOSING REMARKS]
 - NO > Please remember not to eat for at least 8 hours before your appointment. You may drink water during this time. We also want to remind you to collect your urine sample(s) that morning and bring it. We will be mailing out a reminder card. [GO TO CLOSING REMARKS]

[CLOSING REMARKS FOR OFFICE VISIT] Don't forget to bring all your medications with you to your appointment. [For children – Don't forget to note the dates of (his/her) vaccinations. We will be asking about that.] Please let us know as soon as possible if you have to cancel your appointment. You can call at [STUDY TELEPHONE NUMBER] if you have to cancel your appointment. Thank you for being part of our study.

[CLOSING REMARKS FOR HOME VISIT] Don't forget to gather all your medications for your appointment. [For children – Don't forget to note the dates of (his/her) vaccinations. We will be asking about that.] Please let us know as soon as possible if you have to cancel your appointment. You can call at [STUDY TELEPHONE NUMBER] if you have to cancel your appointment. Thank you for being part of our study.

Note: This script cannot be used as a voicemail message.

Multi-site Study Appointment tracking form

Adult Study ID No.	Order	Drder		Completed		Clinic or In-field	
 Child Study ID No. 	Assigned by Coordinator	Comments	Date mm/dd/yy	Time hh:mm	0 cl 1 ha	'inic ome	
Informed Consent	1.		_ _ / _ _ / _ _	AM _ _ : _ PM	0	1	
Update Contact Information	2.		_ _ / _ _ / _ _	AM _ _ : _ PM	0	1	
Blood Draw/ Urine Collection	[]		_ _ / _ _ / _ _	AM _ _ : _ PM	0	1	
Assess Current Medication	[]		_ _ / _ _ / _ _	AM _ _ : _ PM	0	1	

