Section F: Child's Medical History

F1. Have you ever been told by a doctor or other health care provider that your child has or had any of the following medical conditions? Fill out the table below. Circle appropriate response and ask the respondent to specify as directed.

м	edical condition		If yes, what year was your child diagnosed?
-		Yes (Please specify)	year
a. Ca	ancer?	No Don't know	
b. All	lergies?	Yes (Please specify) No Don't know	year
c. At	copic dermatitis/eczema?	Yes (Please specify) No Don't know	year
d. As	sthma?	Yes No Don't know	year
e. Ch (rł	nronic stuffy/runny nose hinitis/sinusitis)?	Yes No Don't know	year
f. Hi	gh cholesterol?	Yes No Don't know	year
g. Th	nyroid disease?	Yes (Please specify) No Don't know	year
h. De	elayed puberty?	Yes (Please specify) No Don't know	year
i. Ot	besity?	Yes No Don't know	year
j. Lu	ipus	Yes No Don't know	year
k. Ce	eliac disease	Yes No Don't know	year
l. Cr	ohn's disease	Yes No Don't know	year
m. Di	abetes	Yes, Type 1 Yes, Type 2 Yes, Type unknown No Don't know	year

	Medical condition		If yes, what year was your child diagnosed?
n.	Scleroderma	Yes No Don't know	year
0.	Attention deficit hyperactivity disorder (ADHD) or attention deficit disorder (ADD)?	Yes No → go to p Don't know → go to p	year
p.	How is your child treated for ADHD or ADD?		year
q.	Other learning or behavioral problems?	Yes (Please specify) No \rightarrow go to Question F2. Don't know \rightarrow go to Question F2.	year
r.	How is your child treated for their learning or behavioral problems?		

F2. What age was your child last vaccinated for:

Diphtheria, Tetanus, Pertussis ("DTaP")	age	Don't know	never was vaccinated
"Tdap" booster Tetanus, Diptheria, Pertussis	age	Don't know	never was vaccinated
Measles, Mumps, Rubella ("MMR")	age	Don't know	never was vaccinated
Tetanus shot (for a puncture wound or cut)	age	Don't know	never was vaccinated

FOR GIRLS ONLY

F3. Has your daughter ever used an oral contraceptive ("birth control pill")?

- ____Yes
- ___No \rightarrow go to Question F5
- ____Don't know \rightarrow go to Question F5
- ____Refused to answer \rightarrow go to Question F5

F4. When did your daughter last use an oral contraceptive ("birth control pill")?

___ Month/Year

F5. At what age did your daughter begin menstruation (have her first period)?

___Age

- ____Has not yet begun to menstruate \rightarrow go to Section G
- ____Don't know
- F6. Does your daughter's period occur regularly (every month)?

____Yes

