Attachment 17a.

Medical Condition	Record Located (Comments)	
g. Liver disease?	Yes (Please specify diagnosis) No	
h. Kidney disease?	Yes (Please specify diagnosis) No	
i. Diabetes?	Yes (Please specify diagnosis) No	
j. Gestational diabetes?	Yes No	
j. Osteoarthritis?	Yes (Please specify diagnosis) No	
k. Osteopenia or Osteoporosis? Yes (Please specify diagnosis) No		
I. Ulcerative colitis?	Yes No	
m. Rheumatoid arthritis?	Yes No	
n. Autoimmune disease? (i.e. Lupus, Multiple sclerosis, Emphysema, Fibromyalgia, Celiac Disease, Crohn's Disease)	Yes (Please specify) No	
o. Endometriosis?	Yes No	
p. Asthma? Yes No		
q. Cancer?	. Cancer? Yes (Please specify) No	
r. Other cancer?	Yes (Please specify) No	

Multi-site Study Medical Record Abstraction Form Child

Form Approved OMB No. 0923-XXXX Exp. Date xx/xx/201x

ATSDR estimates the average public reporting burden for this collection of information as 20 minutes per response, including the time for reviewing instructions, searching existing data/information sources, gathering and maintaining the data/information needed, and completing and reviewing the collection of information. An agency may not conduct or sponsor, and a person is not required to respond to a collection of information unless it displays a currently valid OMB Control Number. Send comments regarding this burden estimate or any other aspect of this collection of information, including suggestions for reducing this burden to CDC/ATSDR Information Collection Review Office, [name]; ATTN: PRA (0923-xxxx).

Medical Record Abstraction Form - Child

Study ID: []	Participant Name: []	Date of Birth://	SSN: xxx-xx-xxxx
--------------	----------------------	------------------	------------------

The person named above, or his or her legal representative, has authorized you to release his or her medical records to ATSDR/[insert institution name] for research purposes. Please check If you have a record that a doctor or other health care provider diagnosed or is treating any of the following medical conditions.

Please fill out the table below. Circle appropriate response and specify requested details as directed. Thank you.

		Year of
Medical Condition	Record Located (Comments)	Diagnosis or
		Treatment
a Allergies?	Yes (Please specify diagnosis)	
	No	
h Atonic dormatitic/oczoma2	Yes	
	No	
c Asthma?	Yes	
C. Astima:	No	
d Rhinitis?	Yes	
u. minus:	No	
	Yes	
e. High cholesterol?	No	

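### Child vaccine antibodies: F2 records only an unverified age at last dose, with no dates, dose count or source, and Sections 2.5.2 and 3.7.1 name different antigens

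*Protocol*

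**What the plan says.** **Hypothesis.** Section 2.5.2, child hypothesis 7, expects higher PFAS to go with lower antibody responses to "rubella, mumps, and diphtheria vaccines".

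**Measurement.** Section 3.6.2.4 fixes a single draw: "This study plans for a one-time 23-ml (5 teaspoons) volume of fasting blood collected". The assay list in Section 3.7.1 covers "antibodies to measles, mumps, rubella, tetanus, and" diphtheria, and Attachment 2 repeats it ("Antibodies to measles, mumps, rubella, tetanus, and diphtheria"). A later sentence in Section 3.7.1 says the study will "measure IgG antibodies for measles, rubella, and diphtheria to determine vaccine responses".

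**Vaccination data.** Section 3.6.5.1 promises a vaccination history. Item F2 on the long form (Attachment 15) and short form (Attachment 15a) reads "F2. What age was your child last vaccinated for". It has four rows (DTaP, Tdap booster, MMR, tetanus shot), each with an age blank, a don't-know option and a never-vaccinated option. The reminder script (Attachment 8) tells parents: "Don't forget to note the dates of (his/her) vaccinations. We will be asking about that".

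**Verification.** Section 3.6.5.1 limits medical record confirmation to reported diseases and conditions. The abstraction forms accordingly ask the provider "Please check If you have a record that a doctor or other health care provider diagnosed" or is treating a listed condition. Neither the child form (Attachment 17b) nor the school record form (Attachment 18b) has an immunisation entry.

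**The concern.** With one blood sample taken at no fixed interval after vaccination, the response to a vaccine is a single level on a declining curve. Where a child sits on that curve depends on time since the last dose and on how many doses were given. Section 3.10 makes estimated cumulative PFAS serum level the primary exposure. That quantity can rise with age while antibody wanes between doses, so a negative association could arise with no PFAS effect.

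The protection is good data on timing and number of doses. F2 gives coarse timing from an unverified source and does not ask for number of doses. An analysis plan written later cannot recover what no form collected.

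The antigen lists are a second, smaller problem. As written, mumps is hypothesised but left out of the response sentence, and measles is in the response sentence without being hypothesised.

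**Working it through.** Table 1 gives no sample size or effect size for vaccine antibodies, so there is no plan figure to reproduce. The check is mainly a comparison of forms, plus an illustration of scale.

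**1. What can be derived from the forms**

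- Time since last dose: the draw date (Attachment 14, item 9a) and date of birth (Attachment 15, A3) give age at draw. Subtracting the F2 age gives an approximate time since last dose for each vaccine. F2 prints no unit or precision for the age.
- Number of doses: not asked. Separate DTaP and Tdap rows give partial information for diphtheria and tetanus. For MMR, the age at last dose is at best an indirect sign of a second dose.
- Source: no field shows whether an answer came from a record or from memory. Parents are told to note dates, but no form has a place for them.
- Elsewhere in the questionnaire, month and year are asked for last contraceptive use, transfusions, residence, day care and school. Coarse timing is specific to this item.

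**2. Antigens side by side**

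| Antigen | 2.5.2 hypothesis | 3.7.1 assay list and Attachment 2 | 3.7.1 response sentence |
|---|---|---|---|
| Rubella | yes | yes | yes |
| Diphtheria | yes | yes | yes |
| Mumps | yes | yes | no |
| Measles | no | yes | yes |
| Tetanus | no | yes | no |

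**3. Scale of residual confounding by waning (all inputs assumed)**

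A simulation of 400,000 children aged 4 to 17 assumed:

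- no PFAS effect;
- log antibody falling 0.1 residual SD per year since last dose;
- PFAS correlated 0.3 with time since last dose;
- last dose at age 4 to 6 for 90% of children older than 5, and at 1 to 1.5 years otherwise;
- reported age at last dose cut to whole years after adding recall error.

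The unadjusted PFAS coefficient should be -0.1 × 0.3 × SD(time since dose). The run gave -0.117, which implies an SD of 0.117/0.03 = 3.9 years.

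| Recall error SD (years) | Adjusted for reported time since dose | Current age also in model |
|---|---|---|
| 0 | -0.001 | -0.001 |
| 0.5 | -0.003 | -0.003 |
| 1 | -0.008 | -0.006 |
| 2 | -0.027 | -0.012 |
| 3 | -0.046 | -0.014 |

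Reported time since dose removes between 1 - 0.046/0.117 = 61% and 1 - 0.001/0.117 = 99% of the spurious coefficient. With age added, the worst case removes 1 - 0.014/0.117 = 88%.

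**4. Against what the study can detect**

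With 2,000 children in quartiles, 500 per group detect (1.96 + 0.84) × √(2/500) = 0.18 SD (two-sided 0.05, 80% power). To put the coefficients on that scale, assume PFAS is roughly normal. The means of the top and bottom quarters then lie 2 × 0.318/0.25 = 2.54 SD apart. The spurious top-versus-bottom difference is 0.117 × 2.54 = 0.30 SD unadjusted, 0.046 × 2.54 = 0.12 SD in the worst adjusted case, and 0.014 × 2.54 = 0.04 SD with age added.

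The simulation does not address number of doses.

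**The case against.** The strongest reply is that F2 already collects the variable that matters. Age at last dose, date of birth and draw date give time since dose, and adjusting for it removes most of the waning effect in the illustration. Parents are also prompted beforehand, so answers need not be pure recall. This stands. A reader might infer from F2 that waning cannot be separated from PFAS at all. The documents do not support that; the adjustment is imprecise and unverified, not impossible.

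Second, if age is what links PFAS and time since dose, conditioning on age closes that path. Late, missed or extra doses then bias the PFAS coefficient only if they relate to PFAS given age, and otherwise mainly add noise. The same holds for number of doses. This also stands: the documents give no reason to expect such a link. They give no means of checking for one either.

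Third, the antigen mismatch could be read as leaving the mumps hypothesis untestable. It does not, because mumps is assayed under both Section 3.7.1 and Attachment 2, and F2 covers MMR. One sentence needs reconciling.

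Fourth, choice of covariates and handling of don't-know answers can be left to an analysis plan, and Section 3.10 already has a change-in-estimate rule for confounders. That is fair, but the rule can act only on variables that were collected.

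**Conclusion.** The point holds as a data-collection gap and a wording contradiction. Adjustment for time since last dose will be approximate and cannot be checked against records. Number of doses cannot be adjusted for directly, apart from the partial information in the separate DTaP and Tdap rows. Sections 2.5.2 and 3.7.1 disagree on mumps versus measles.

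The size is modest if parents answer well and grows with recall error: a residual of -0.001 to -0.046 SD per SD of PFAS, against -0.117 unadjusted. These figures rest wholly on assumed waning, correlation and recall error. They show scale and do not predict the study's bias.

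A reader might also compound an assumed antibody decline of 10 to 30% per year over a three-year uncertainty in dose timing (1 - 0.9³ = 27% to 1 - 0.7³ = 66%) and treat the result as the bias. It is the gap between two individual children at opposite ends of that window, at a rate the documents do not give. It is not bias in an association.

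The change is worth making before fielding because it is cheap and the information cannot be recovered by later analysis of the forms.

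**What to change.** 1. **F2, both forms:** record the date of each DTaP, Tdap, Td and MMR dose, and whether it came from a record or from memory. This gives the dates parents are told to note a place to go.
2. **Attachment 17b:** add the same dose dates from the provider's record. Permission to access the child's medical records is already sought (Section 3.6.2.2).
3. **Sections 2.5.2 and 3.7.1:** use one antigen list for the vaccine-response hypothesis, and say what role the remaining assayed antigens have.
4. **Analysis, in the protocol or analysis plan:** use time since last dose and number of doses as covariates and keep all children in. Treat restriction to record-documented doses as a sensitivity analysis only, since it may select children by access to care.

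The cost is a few form lines, wording, and some parent and provider time. Records for all children would also mean sending 17b for those with no reported condition, which adds to the provider workload.
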